5.1 PRIMARY ENDPOINT(S)

The primary endpoint is the occurrence of treatment-emergent adverse events (TEAEs) up to the end of the maintenance treatment period including REP (i.e., 16 weeks after the last study treatment).

5.2 SECONDARY ENDPOINT(S)

5.2.1 Key secondary endpoint(s)

Not applicable.

[figure not shown]
5.2.2 Secondary endpoint(s)

[figure not shown]
Secondary endpoints are defined as described below:

[figure not shown]
- Percent change in [REDACTED] abscess and inflammatory nodule (AN) count from baseline (%) up to Week [REDACTED]
- Percent change in [REDACTED] draining fistula (DF) count from baseline (%) up to Week [REDACTED] (*Only patients with at least 1 draining fistula at baseline will be used for analysis*).
- Hidradenitis suppurativa Clinical Response (HiSCR) up to Week [REDACTED]
- Change from baseline in International Hidradenitis suppurativa Severity Score System (IHS4) value up to Week [REDACTED]
- Hidradenitis suppurativa Physician Global Assessment (HS-PGA) score of 0 or 1 up to Week [REDACTED]
- Absolute change from baseline in Hidradenitis suppurativa Area and Severity Index (HASI) score up to Week [REDACTED]
- At least one flare (defined as at least [REDACTED] in AN count with a minimum [REDACTED])

[figure not shown]
Proprietary confidential information © 2024 Boehringer Ingelheim International GmbH or one or more of its affiliated companies.

- of [redacted] relative to baseline) up to Week [redacted]
- At least [redacted] from baseline in Numerical Rating Scale (NRS30) in Patient's Global Assessment of HS Pain up to Week [redacted]

6. GENERAL ANALYSIS DEFINITIONS

6.1 TREATMENT(S)

For basic study information on the treatment to be administered, assignment to treatment, and selection of dose, cf. Section 4 of the CTP.

The study phases are defined relative to first dose at Day 1 as below:

Table 6.1: 1 Flow chart of analysis phases of the study

Study analysis phase	Description	Start (included)	End (included)
Screening phase	Screening	Earliest of (Date of informed consent, first screening procedure)	Date/time of start of the first study dose minus 1 second.
Treatment phase & Residual effects period	On-treatment period	Date/time of start of the first study dose regardless of infusion or injection (Day 1)	Earliest of: i) Date of last study drug regardless of infusion or injection + 112 days at 23:59, ii) cut-off for interim analysis if applicable.
Follow-up phase ¹ (if applicable)	Off-treatment period (if applicable)	Date of end of last study dose + 113 days at 0:00 a.m.	Latest of: i) Date of EOS visit; ii) last contact date on trial termination page at 11:59 p.m.

Dates are defined individually per patient. If more than one date is associated with a specific visit, measurements associated with a specific date are assigned to a study analysis phase according to the rules specified in the table. An analysis phase will not extend beyond the start date of the following phase.

¹ The off-treatment period (i.e. Follow-up phase) only exists if the date of EoS visit or the last contact date is after the date of end of last administration + 112 days.

Treatments will be labelled for final analysis as follows:

Tables will be displayed also by prior treatment from parent trial for final analysis:

- “Prior Placebo” (applicable to analysis for whole on-treatment period, i.e., including infusion loading at Day 1 for placebo patients from parent trial]
 - “Prior Placebo + uptitration at Week [] (applicable to analysis for whole on-treatment period, i.e., including infusion loading at Day 1 for placebo patients from parent trial and after dose escalation]
 - “Prior Placebo + Other” (applicable to analysis for whole on-treatment period, i.e., placebo patients from parent trial who received [] dose [] during all [] period or who were early discontinued before Week [])

- “Prior Speso” (applicable to analysis for whole on-treatment period, i.e., including [REDACTED] at Day 1 for speso patients from parent trial, before and post dose escalation)
 - “Prior Speso + uptitration at Week [REDACTED]” (applicable to analysis for whole on-treatment period, i.e., including [REDACTED] at Day 1 for speso patients from parent trial and after dose escalation)
 - “Prior Speso + Other” (applicable to analysis for whole on-treatment period, i.e., speso patients from parent trial who received [REDACTED] during all [REDACTED] [REDACTED] or who were early discontinued before Week [REDACTED])

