6.4 SUBJECT SETS ANALYSED

The following analysis sets will be defined for this trial:

Enrolled Set (ES)

This patient set includes all patients who signed informed consent. It will be used for analyses of patient disposition.

Safety Analysis Set (SAF):

This patient set includes all patients who received at least one dose of study drug in trial 1368-0067. This is the main analysis set for efficacy and safety. Patients will be analyzed according to the actual treatment received.

Safety Set ADA (SAF-ADA)

This patient set includes all patients who received at least one dose of study drug and had at least one evaluable ADA sample in trial 1368-0067. This is the main analysis set for ADA impact on efficacy and safety. Patients will be analyzed according to the actual treatment received.

The discussion of all exceptional cases and problems and the decisions on the allocation of patients to populations will be made at the RPM/DBLM at the latest.

Table 6.4: 1 Overview of use of patient analysis sets by class of endpoint and handling of estimand and missing data

Class of endpoint	
	ES SAF
Disposition	OR
Compliance and exposure	OR
iPD	OR
Demographic/baseline characteristics	OR
Concomitant medication	OR
Primary endpoint	OR
Secondary binary efficacy endpoints	OC-NRI: for binary efficacy endpoints
Secondary continuous efficacy endpoints	OC for continuous efficacy endpoints.
Further efficacy endpoints	OC for continuous efficacy endpoints. OC-NRI: for binary efficacy endpoints
Plasma concentration & ADA	OR
Efficacy endpoints by ADA impact	OC for continuous efficacy endpoints OC-NRI for binary efficacy endpoints
AE	OR
Lab data, vital signs	OC-IR

For explanation of the different approaches with regard to missing data see [Section 6.6](#).

[figure not shown]
OC = observed cases excluding values after any use of rescue medication.

OC-IR = observed cases including also values after any use of rescue medication.

OC-NRI = values after any use of rescue medication will be censored and impute with non-responder..

OR = original results.

NRI = Non-Response Imputation, cf. [Section 6.6.2](#).

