7. PLANNED ANALYSIS

Final trial analysis is planned to be performed at the end of the study once all patients have completed the study (including any follow-up period) if applicable. As specified in CTP in Section 7.2.7, multiple interim analyses may be done over the 2-year conduct phase of this trial. The corresponding snapshot will be taken for the interim analysis and data only up to the cut-off will be included into the analysis.

First interim analysis up to Week [REDACTED]

The interim analysis is planned after all patients in current study finishing their Week [REDACTED] visit or early discontinued before the visit, and a snapshot will be performed. All data collected up to Week [REDACTED] dosing will be included in this interim analysis.

Final analysis

Final trial analysis will be performed once all patients have completed the trial; at that time point, a final database lock will be done.

General Remarks

The format of the listings and tables will follow the BI guideline "Standards for Reporting of Clinical Trials and Project Summaries" (9) and those generated for PK will follow BI guideline "Standards and processes for analyses performed within Clinical Pharmacokinetics/Pharmacodynamics" (11).

The individual values of all patients will be listed, including those collected during the off-treatment period. Listings will generally be sorted by country, centre number, patient number and visit (if visit is applicable in the respective listing). AE listings will be sorted by assigned treatment (see [Section 7.8.1](#) below for details). The listings will be contained in Appendix 16.2 (SDL) of the CTR.

The following standard descriptive statistical parameters will be displayed in summary tables of continuous variables:

N:	number of non-missing observations
Mean:	arithmetic mean
SD:	standard deviation
Min:	minimum
Q1:	lower quartile
Median:	median
Q3:	upper quartile
Max:	maximum

For PK analyte concentrations, the following descriptive statistics will additionally be calculated: variables:

CV: arithmetic coefficient of variation
gMean: geometric mean
gCV: geometric coefficient of variation

The data format for descriptive statistics of concentrations will be identical with the data format of the respective concentrations.

Statistical parameters will be displayed to a defined number of decimal places as specified in the BI guideline "Standards for Reporting of Clinical Trials and Project Summaries" (9).

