Tabulations of frequencies for categorical data will include all possible categories and will display the number of observations in a category as well as the percentage (%) relative to the respective treated patient set. Percentages will be rounded to one decimal place. The category missing will be displayed if and only if there are actual missing values. Percentages will be based on all patients in the respective patient set whether they have non-missing values or not unless there is another particular specification.

Disposition of the patient population participating in the trial will be summarised by presentation of the frequency of patients enrolled, treated, enrolled but not treated, who completed all doses of trial medication as planned, who completed the trial (EOS), who prematurely discontinued study treatment, by reason and who withdrew from the trial, by reason. Summary statistics of patients who did the dose modification at Week 12 and patients who discontinued due to no change observed at Week 24 after dose modification (according to Table 3.1: 1 in CTP) will be also displayed. The frequency of patients with iPDs will be presented; iPDs will be listed per patient.

To better illustrate the long-term disposition of entire maintenance treatment (cf. [Section 6.1](#)), a summary table regarding patient status over time will be added. The cumulative frequency of patients for the following categories will be displayed based on ■-week intervals:

- Ongoing on study medication, i.e., without early treatment discontinuation by the time point
 - Intake of rescue medication
 - Up-titrate the dose to ■
 - Any of the above
- Pre-maturely stopped study medication, i.e., discontinued study medication by the time point
 - Intake of rescue medication
 - Up-titrate the dose to ■
 - Any of the above
- Ongoing but not achieved the visit, if due to the cut-off of interim analysis
 - Intake of rescue medication
 - Up-titrate the dose to ■

- Any of the above

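### In the visible SAP, the '+ uptitration' safety labels run from Day 1 and nothing is split at escalation, so AEs and exposure on the escalated dose are not summarised separately

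*SAP*

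**What the plan says.** SAP 6.1 states that "Tables will be displayed also by prior treatment from parent trial for final analysis" and lists sub-groups under each parent arm. The prior-placebo '+ uptitration' label covers the whole on-treatment period, "including infusion loading at Day 1 for placebo patients from parent trial and after dose escalation"; the prior-spesolimab label is built in the same way. The '+ Other' groups hold patients not escalated, "or who were early discontinued before Week" (week number redacted). Table 6.1: 1 defines one on-treatment phase, from first dose to last dose plus 112 days, with no boundary at escalation.

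The primary endpoint (SAP 5.1) is TEAE occurrence "up to the end of the maintenance treatment period including REP". SAP 7.8 reports safety for the overall on-treatment period. SAP 7.8.1 counts time at risk from the first treatment in this study, as protocol 7.2.5 does. SAP 7.7 splits dose only into loading and maintenance stages.

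The text is not uniform on which grouping the AE outputs use:
- SAP 7.8.1 tabulates AEs by parent-trial treatment and, for registry disclosure, by treatment.
- SAP 7 says "AE listings will be sorted by assigned treatment".
- SAP 6.4 says "Patients will be analyzed according to the actual treatment received".

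SAP 7 also counts "patients who did the dose modification at Week 12" and says "a summary table regarding patient status over time will be added", which includes up-titration.

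**The concern.** Long-term safety is the primary objective, and protocol Table 3.1: 1 changes the dose at Week 12 in patients selected on response. A reader of the safety tables will want to know which AEs arose on the escalated dose and over how much exposure. Protocol 5.2.6.1.6 itself lists an indication of dose-response among the arguments for causality.

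A group defined by a Week 12 decision but counted from Day 1 raises two problems. Events and person-time before escalation are credited to it. A patient must also still be on treatment at the decision to enter it, so AE discontinuations before that point can only be counted in '+ Other'. The disposition table shows how many patients remain on the escalated dose, but gives neither person-time nor AEs by dose.

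**Working it through.** The plan states no figure to reproduce. All event and discontinuation rates below are assumed.

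**1. Time window.** Visit 8 is at Week 14 and visits are every 2 weeks (protocol flow chart). Visit 52 is then at 14 + 2 × 44 = Week 102 and EoT at Week 104. Adding the 16-week REP gives 120 weeks (840 days). Up-titrated non-responders can be stopped at Week 24 (protocol 3.3.4.1), giving 40 weeks (280 days). The 12 pre-escalation weeks are 12/120 = 10% to 12/40 = 30% of the window.

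**2. EAIR under the '+ uptitration' label.** Let L be the yearly hazard before escalation and rL after it, with t1 = 84/365.25 years and T the window.
- p1 = 1 − exp(−L·t1)
- p2 = exp(−L·t1) × [1 − exp(−rL(T − t1))]
- EAIR = 100 (p1 + p2) / (p1/L + p2/(rL))

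| Pre-escalation rate per 100 PY | 10 | 50 | 100 |
|---|---|---|---|
| r = 2: true escalated rate | 20 | 100 | 200 |
| 120 weeks | 18.8 | 89 | 166 |
| 40 weeks | 16.9 | 82 | 156 |
| r = 0.5: true escalated rate | 5 | 25 | 50 |
| 120 weeks | 5.5 | 28 | 58 |
| 40 weeks | 6.5 | 33 | 68 |

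Doubling reads 6–17% low over 120 weeks and 16–22% low over 40. Halving reads 11–17% high and 31–36% high. With r = 1 there is no bias.

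**3. Crude percentages.** The whole-period figure, 1 − exp(−L·t1 − rL(T − t1)), can never be below the escalated-period figure, 1 − exp(−rL(T − t1)). At 50 per 100 PY and r = 1 it is 68% against 64% over 120 weeks, and 32% against 24% over 40.

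**4. AEs that end treatment, with no dose effect.** Take AE-discontinuation hazard h = 0.3/year, other discontinuation d = 0.15/year, and half of those on treatment at Week 12 up-titrated at random.
- Up-titrated: (0.3/0.45) × [1 − exp(−0.45 × 1.763)] = 36.5%, where 1.763 years is Week 12 to Week 104.
- AE stops before Week 12: (0.3/0.45) × [1 − exp(−0.45 × 0.230)] = 6.6% of all patients; 90.2% are still on treatment.
- Other: (0.0656 + 0.5 × 0.902 × 0.365) / (1 − 0.5 × 0.902) = 41.9%.
- Ratio: 36.5/41.9 = 0.87, although the dose has no effect.

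Simulation over h = 0.1–0.5 and 30–70% up-titrated gives ratios of 0.77–0.92 as frequency and 0.60–0.82 as EAIR. Counting from Week 12, both are 1.00.

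**5. Precision.** With d = 0.15, 45 × exp(−0.15 × 0.230) = 43.5 patients are on treatment at Week 12; 30–70% of them is 13–30. Each contributes [1 − exp(−0.15 × 1.763)]/0.15 + 112/365.25 = 1.86 years, so the escalated period holds about 24–56 PY. Zero events leave an upper 97.5% limit of 3.69/24.1 = 15 to 3.69/55.7 = 6.6 per 100 PY. At a true 50 per 100 PY the expected exact 95% interval is about 21–100 with 13 patients and 30–79 with 30. Even the narrower interval runs from about 40% below to 58% above the true rate, against a 120-week bias of at most 17%.

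**The case against.** The strongest objection is that the gap sits where text is missing. In this copy nothing follows the sentence introducing the final-analysis treatment labels, and the quoted labels come under a line saying tables are displayed *also* by prior treatment. That makes them a second set. SAP 5.4 and 6.5 are not shown. A dose-based label or period may be defined there, so a reader who inferred that the plan has no safety analysis by dose would go further than the documents allow. This stands. A label alone would not move the stated EAIR clock or safety period, but a hidden period definition could. The sponsor's AE-handling standards and the DMC's own analysis plan cannot be checked either.

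Three further points also stand:
- Individual values are to be listed and AE start dates are collected, so with about 45 patients the events on the escalated dose could be reconstructed by hand.
- SAP 3 plans an interim once all patients reach Week 12. If its cut-off (redacted in SAP 7) is Week 12, it may summarise the pre-escalation period. It would not give an escalated-dose rate.
- Whole-period tables match the primary endpoint, and the EAIR clock follows the protocol. Neither is an error.

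The objection that a split is only a preference is weaker. SAP 7.9.2 already plans a before/after split of safety events around ADA development, because timing matters there. The same reasoning applies to a change of dose.

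**Conclusion.** The point holds as a modest improvement, conditional on the text not shown. On the visible text, either the AE tables use the '+ uptitration' and '+ Other' labels, in which case they mix dose periods and the two columns are not comparable, or they use only the parent-arm columns, in which case no summary AE rate on the escalated dose is produced.

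A reader might infer that the plan understates harm on the escalated dose. The documents do not support that. The direction depends on whether risk rises, stays the same or falls after escalation, which is unknown. The EAIR sizes rest on assumed constant hazards and a Week 104 EoT derived from visit numbering. Step 4 assumes random up-titration, whereas the protocol selects on response, so it shows only the structural part of the difference, and it matters only if the two columns are compared; no such test is planned. Over a full 120 weeks the EAIR bias is smaller than sampling error. What is gained is a view of AEs and exposure by dose.

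**What to change.** 1. State in SAP 7.8.1 which labels the AE tables use, and confirm whether a dose-based period is already defined. Keep the whole-period tables for the primary endpoint.
2. Unless such a period exists, add descriptive AE frequency, EAIR and person-time (SAP 7.7) by dose at onset, split at each patient's first escalated dose, with the first-event clock restarted there.
3. Assign events and the REP to the dose most recently received. Keep AEs ongoing at escalation in the earlier period unless they worsen.
4. Show the pre-escalation time of up-titrated patients separately from the time of patients never up-titrated.
5. Start any display of up-titrated against not-up-titrated patients at the Week 12 decision, and show earlier discontinuations separately.
6. Footnote that the contrast is descriptive and confounded by selection on response, time and carry-over. With the protocol's half-life of about 4 weeks, 0.5^(12/4) = 12.5% of a Day 1 level would remain at Week 12 if kinetics are linear.

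The cost is programming and a few more tables with small numbers. Dosing and AE onset dates are already collected.

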6.2 IMPORTANT PROTOCOL DEVIATIONS

Data discrepancies and deviations from the CTP will be identified for all patients in the database (i.e., enrolled patients). Consistency check listings (for identification of violations of time windows) and a list of protocol deviations will be provided to be discussed at the RPM/DBLM/ CQM. At this meeting, it will be decided whether a discrepant data value can be used in analyses or whether it must be queried in the clinical database. Each protocol deviation must be assessed to determine whether it is an important Protocol Deviation (iPD). For definition of iPDs, and for the process of identification of these, refer to the BI reference document "Identify and Manage Important Protocol Deviations (iPD)" (3).

If any iPDs are identified, they are to be summarised into categories and will be captured in the RPM/DBLM/CQM minutes via an accompanying Excel spreadsheet (3). The following table contains the categories which are considered to be iPDs in this trial. If the data show other iPDs, for example, based on monitor visits to the sites, then this table will be supplemented accordingly by the time of the RPM/DBLM/CQM. Not all iPDs will lead to exclusion from analysis sets. Certain iPDs may lead patients to being excluded from all the analyses.

As this is an open label, long term safety trial, all analyses will be performed based on the treated population only. Since no confirmatory efficacy testing is planned, no efficacy related iPDs leading to exclusion from analysis set are defined.

6.3 INTERCURRENT EVENTS

The expected intercurrent events (ICEs) of interest in this trial are:

- Use of rescue therapy (while still on treatment), as defined in [Section 5.4.3](#)
- Treatment discontinuation without restricted medication, flagged by medical review if occurring
- Treatment discontinuation with restricted medication, flagged by medical review if occurring

The strategies for handling intercurrent events in this trial are as follows:

Hybrid Strategy (EC-H): All intercurrent events except for the administration of rescue therapy will be handled using the treatment policy approach. Rescue therapy will be handled

using the hypothetical approach, under the scenario in which the intercurrent event would not occur. This will be used as the **primary strategy** of implementing the Estimand Concept (EC), allowing the effects of adherence, i.e., regardless of treatment discontinuation, but excluding the effects of rescue therapy.

No deaths are expected in this trial. In the unlikely event of a death occurring, it will be handled using a hypothetical approach for each strategy.

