There were no relevant changes compared to placebo for laboratory safety, including clinical chemistry, haematology, coagulation parameters, and urinalysis. No clinically relevant changes were observed in 12-lead electrocardiogram (ECGs), vital signs, and cardio-monitoring. Pharmacokinetics (PK) analysis showed that exposure (AUC_{0-tz} and C_{max}) to spesolimab increased with increasing dose in an approximately dose-proportional manner from 0.3 to 10 mg/kg.

The effective half-life of spesolimab is approximately 4 weeks in the linear dose range. Overall, PK data so far suggests target-mediated drug disposition kinetics for spesolimab. Anti-drug antibodies (ADA) were detected in 8 patients, 3 of those had pre-existing levels. Pharmacodynamic (PD) effects in this First in Human Single Rising Dose (SRD) trial [c03361085] were assessed by indirect target engagement of IL36R by spesolimab using an ex-vivo whole blood stimulation assay. Preliminary analyses indicate that $\geq 94\%$ peripheral IL36R receptor occupancy is achieved with doses ≥ 0.05 mg/kg from 30 minutes post infusion to 10 weeks.

In a multiple rising dose (MRD) trial, spesolimab or placebo have been administered to healthy volunteers at multiple ascending i.v. doses of 3, 6, 10 and 20 mg/kg given qw for 4 weeks (i.e. 4 administrations) or a single dose of 20 mg/kg (8 subjects each, 3:1 on active or placebo). Overall, spesolimab was well tolerated. There were no dose dependent AEs, AEs considered to be dose limiting and no SAEs. In all cases the AEs were of mild or moderate intensity. Furthermore, there were no clinically relevant abnormalities on treatment with spesolimab with respect to safety laboratory, vital signs, or ECGs as assessed by a central reader. For further details and most recent results refer to the current Investigator's Brochure (IB) [c03320877-10].

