1.2.3 Residual Effect Period

The Residual Effect Period (REP) of spesolimab is 16 weeks. This is the period after the last dose with measurable drug levels and/or PD effects still likely to be present.

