2. TRIAL OBJECTIVES AND ENDPOINTS

2.1 MAIN OBJECTIVES, PRIMARY AND SECONDARY ENDPOINTS

2.1.1 Main objectives

[figure not shown]
The primary objective of this trial is to assess the long-term safety of spesolimab in patients with HS who have completed the 1368-0052 PoCC trial and are qualified for entry into this trial. The secondary objectives are to evaluate efficacy at a lower dose than tested in PoCC trial.

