3. DESCRIPTION OF DESIGN AND TRIAL POPULATION

3.1 OVERALL TRIAL DESIGN

This open label, single-arm, multi-regimen, 2-year extension study investigates the long-term safety and efficacy of spesolimab in patients with HS who have completed their treatment in the 1368-0052 PoCC trial. BI trial 1368-0052 is the first trial from which patients will rollover into this extension trial. Patients rolling over into this trial must have completed the treatment period as required in the 1368-0052 PoCC trial. Ideally, the end of treatment (EoT) visit of the preceding trial is the baseline visit (V1) of this extension trial.

This extension trial consists of a [REDACTED] weeks treatment period followed by a [REDACTED] week safety follow-up period.

Approximately [REDACTED] patients from the 1368-0052 PoCC trial are planned to be rolled over into this open-label extension study.

Patients from the placebo arm of the 1368-0052 PoCC trial will be given an initial [REDACTED] dose of spesolimab plus [REDACTED] placebo, followed by [REDACTED] spesolimab [REDACTED] every [REDACTED] weeks [REDACTED]). Patients from the active arm of the 1368-0052 PoCC trial will be given an initial [REDACTED] placebo plus [REDACTED] spesolimab [REDACTED], followed by [REDACTED] spesolimab [REDACTED] every [REDACTED]. Administration of trial medication at Visit 1 is blinded. See [Section 3.1.1](#) for more details.

[figure not shown]
At Week [REDACTED] of this extension trial, all patients will be assessed for the change of HS-PGA grade. The change in HS-PGA grade will be compared with the assessment at baseline of this extension trial / Week [REDACTED] of the 1368-0052 PoCC trial. Based on the individual responder status decisions on further dosing will be taken as depicted in [Table 3.1: 1](#).

Table 3.1: 1 Week 12 Dose Modification Management

Baseline	Assessment at Week 12	Management
Status from Week 12 of 1368-0052 PoCC trial	HS-PGA grade change from baseline HS-PGA grade of this trial	
Responder (Achieved HiSCR 50)	No change or improvement in grade (i.e., reduction by at least 1 grade)	Continue the same dose
	Worsening in grade (i.e., increase by at least 1 grade)	Option to increase the dose to [REDACTED]
Partial Responder (Achieved HiSCR 25 but did not achieve HiSCR 50)	Improvement in grade	Continue the same dose
	No change or worsening in grade	Increase the dose to [REDACTED]
Non-responder (Did not achieve HiSCR 25)	Improvement in grade	Continue the same dose

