4.1.2 Selection of doses in the trial and dose modifications

In the 1368-0052 PoCC trial, a fixed rather than weight-based dose regimen was selected. Early trials of therapeutic monoclonal antibodies often investigate bodyweight-based regimens to reduce the inter-subject variability in drug exposure. However, there is generally only a modest contribution of body weight to the overall PK and PD variability of monoclonal antibodies. Furthermore, monoclonal antibodies are highly target specific and offer a relatively large therapeutic window compared to new chemical entities. Therefore, most monoclonal antibodies are approved at fixed doses in antibody/target excess in order to cover target turnover and maximize efficacy [R10-6267; R13-4749; R13-4753; R13-4750; R13-4754].

In this extension trial, patients from the active arm in the parent trial will be given [REDACTED] every [REDACTED], which is half the dose of the 1368-0052 PoCC trial. This is to evaluate whether these patients would be able to sustain efficacy at a lower dose. Patients who were in the placebo arm will be given a [REDACTED] dose of spesolimab, followed by [REDACTED] every [REDACTED]. The rationale is to give an opportunity to the patients from the placebo arm to be given active treatment and also to understand induction response after a placebo period. Additionally, this dose was also selected to evaluate efficacy of [REDACTED] dose. All the patients will be reassessed at Week [REDACTED] to evaluate the response and will have the option of either continuing the same dose or increasing the dose.

Data from the 1368-0052 PoCC trial will not be available prior to the 1st patient rolling over into this extension trial. When new data from the PoCC trial becomes available, the impact for this extension trial will be evaluated and if needed the dose would then be adjusted by amending this protocol.

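### The Week 12 dose increase is not an intercurrent event, so later binary efficacy rows either mix dose levels or are selected on outcome, and no visible display gives lower-dose response over the whole prior arm

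*SAP*

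**What the plan says.** **Objective.** Protocol 2.1.1: "The secondary objectives are to evaluate efficacy at a lower dose than tested in PoCC trial". For patients who had active treatment in the parent trial, Protocol 4.1.2 sets a dose "which is half the dose of the 1368-0052 PoCC trial" and gives the reason: "This is to evaluate whether these patients would be able to sustain efficacy at a lower dose".

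**Dose increase.** Protocol 3.1, Table 3.1: 1 ("Week 12 Dose Modification Management"), combines parent-trial responder status with the change in HS-PGA grade from the extension baseline. Partial responders and non-responders whose grade is unchanged or worse are increased. Responders whose grade worsens have an option to increase.

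**Intercurrent events.** SAP 6.3 ("The expected intercurrent events (ICEs) of interest in this trial are") lists rescue therapy, and discontinuation with or without restricted medication. Rescue gets a hypothetical strategy and everything else treatment policy. The dose increase is not mentioned.

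**Data rules.** Under SAP 6.4 and 6.6.2, the observed-case and non-response rules remove or impute values after rescue only.

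**Rows.** SAP 6.1 defines 'Prior Speso' over the whole on-treatment period: "at Day 1 for speso patients from parent trial, before and post dose escalation". 'Prior Placebo' also covers the whole period. Each has two sub-rows, one for up-titrated patients and one called '+ Other', which holds patients who were not up-titrated together with early discontinuers.

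**Other planned output.** The SAP also plans a Week 12 interim analysis (Sections 3 and 7), counts of patients with dose modification (Section 7), and HS-PGA change by responder status (7.6.3).

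**The concern.** The event that ends lower-dose treatment is itself largely a marker of inadequate response on the lower dose, and it has no stated handling. A patient who does not improve by Week 12, is increased, and then meets HiSCR counts as a success in the whole-arm row. Removing the increased patients does not cure this, because the remaining group was formed by a decision based on outcome after baseline.

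At stake is the reading of the secondary objective. Someone who takes the whole-arm or '+ Other' percentage beyond Week 12 as response on the lower dose would read it too favourably. The primary safety endpoint is untouched, and no error rate is involved because the trial is descriptive.

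**Working it through.** The plan gives no sample size, power or effect figure to reproduce. The check has three parts.

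**1. Does any rule take the increase into account?** SAP 6.3 does not list it. The observed-case rule drops values after rescue, and OC-NRI imputes non-response after rescue. Neither acts on the increase, so post-increase responses stay in a row defined as covering the time before and after escalation.

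**2. How far can the rows differ?** All rates here are assumed. At a visit after Week 12, let
- c = share of the whole treated arm that responds without having been increased,
- u = share of the arm that was increased,
- r = response rate among those increased.

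Then:
- lower-dose response over the whole arm = c
- whole-arm row = c + u × r
- '+ Other' row = c / (1 − u)

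With c = 0.40, u = 0.30, r = 0.40:
- whole-arm row = 0.40 + 0.30 × 0.40 = 0.52
- '+ Other' row = 0.40 / 0.70 = 0.57

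With c held at 0.40, u from 0.10 to 0.50 and r from 0.20 to 0.60:
- whole-arm row: from 0.40 + 0.10 × 0.20 = 0.42 to 0.40 + 0.50 × 0.60 = 0.70
- '+ Other' row: from 0.40 / 0.90 = 0.44 to 0.40 / 0.50 = 0.80

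The direction needs no assumed rate: u × r cannot be negative and 1 / (1 − u) cannot be below 1, so neither row can fall below c. Early discontinuers sit inside 1 − u, so they do not change this.

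**3. Is the period up to Week 12 a clean lower-dose period for prior-spesolimab patients?** Inputs are Protocol 1.2.3 ("The Residual Effect Period (REP) of spesolimab is 16 weeks") and Protocol 1.2.1 ("The effective half-life of spesolimab is approximately 4 weeks in the linear dose range").

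*Timing.* If g is the number of weeks from the last parent dose to Visit 1, extension Week 12 is 12 + g weeks after that dose. This is below 16 unless g is at least 4. Protocol 6.2.1 allows at most 2 weeks from the parent end-of-treatment visit to enrolment, but the time from the last parent dose to that visit is not given.

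*Exposure.* Assume parent steady state at twice the lower-dose level, first-order decay and g = 0. Exposure relative to lower-dose steady state at week t, for half-life h in weeks, is 1 + 2^(−t/h).
- h = 4: Week 4 = 1.50, Week 8 = 1.25, Week 12 = 1.125
- Week 12 at h = 3: 1.06; at h = 5: 1.19

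Carry-over is sizeable in the first weeks and modest by Week 12.

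**The case against.** The strongest reply is that the SAP already separates the groups. It plans up-titrated and '+ Other' rows, a Week 12 interim before any increased dosing, HS-PGA change by responder status, and counts of dose modification. For visits after Week 12, the whole-arm lower-dose figure is the number of '+ Other' responders over the whole arm's N, and a careful reader could build it from the split tables. This largely stands. The missing piece is a stated definition and a display that shows it, not data. A reader might infer that no planned output bears on lower-dose efficacy; the documents do not support that.

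Second, the week to which the secondary endpoints run is redacted and may be Week 12. If so, dose mixing does not reach them and affects only endpoints shown over later visits, such as HiSCR and NRS30 over time, which SAP Section 4 adds. This stands. A reader might infer that efficacy is overstated whatever the redacted week is. Up to Week 12, that would rest on carry-over alone, and about 1.13 times steady-state exposure at Week 12 does not establish an efficacy bias without an exposure-response relation.

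Third, '+ Other' does not remove precisely those who failed on the lower dose. A partial responder with a stable HS-PGA grade is increased without having lost anything, and a worsening responder may stay on the lower dose. This also stands. The selection is largely, not wholly, on outcome, and a rule counting the increase as non-response is conservative.

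Finally, some SAP sections are not visible in the text, so the absence of a suitable display can be asserted only for what can be read.

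**Conclusion.** The point holds for binary efficacy endpoints displayed beyond Week 12. The whole-arm rows credit responses gained on the increased dose, and the '+ Other' rows are selected largely on Week 12 outcome and include early discontinuers. No display visible in the text gives response on the lower dose with all treated patients of the prior arm in the denominator. The Week 12 interim and the split rows give partial information. Displays limited to Week 12 are free of dose mixing.

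The direction is certain: both rows are at or above the whole-arm lower-dose figure. The size is not known. The 52% and 57% against 40%, and the ranges around them, rest on assumed rates.

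For prior-spesolimab patients, Week 12 may lie inside the residual effect period of the last parent dose, with about 1.06 to 1.19 times lower-dose steady-state exposure at half-lives of 3 to 5 weeks, assuming parent steady state and no gap. A reader might infer that Week 18, the first scheduled lesion count more than 16 weeks after Visit 1, is the first clean readout. The documents do not support fixing that cut-off, because the residual period runs from the last parent dose and its date is not given.

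**What to change.** In SAP 6.3, name the Week 12 dose increase as an intercurrent event for the lower-dose objective. Then:

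- **Binary efficacy endpoints:** add one supplementary display over time by prior arm. Count visits after the increase as non-response on the lower dose, keep the full treated arm as denominator, and show the number up-titrated alongside. For the flare endpoint, state the direction explicitly, since there the coded event is the unfavourable outcome.
- **Continuous endpoints:** label any lower-dose display as while on the lower dose and therefore selected, and show the number remaining at each visit. Dropping post-increase values does not remove the selection.
- **Existing tables:** keep them, labelled as results of the titration regimen.
- **Prior-spesolimab arm:** add a note that Week 12 may fall within 16 weeks of the last parent dose, without setting a fixed cut-off week.

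The cost is SAP wording and one more table from data already collected; no dosing rule changes. The lower-dose response figure will be less favourable, and conservative, because stable partial responders who are up-titrated count as non-responders. A footnote should say so.
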